11.4.3. Safety Analyses

All safety endpoints will be summarized descriptively using the safety analysis set. If descriptive summaries warrant further exploration of comparisons between treatment groups, then additional safety analyses may be conducted in an *ad hoc* manner.

11.4.3.1. Adverse Events

The primary analysis of AEs will consider only treatment-emergent adverse events (TEAEs), events occurring for the first time, or worsening during or after the first dose of investigational product. Subject incidence of TEAEs and SAEs will be tabulated by Preferred Terms (PTs) and System Organ Class (SOC). Severity and relationship to investigational product will also be presented. For summary tables, a subject who experiences the same coded event more than once is counted only one time for that coded event at the highest severity level. AEs will be presented by descending order of frequency in MedDRA SOC and PT.

Listings of all SAEs, AEs leading to study withdrawal, and deaths on-study will also be included. Duration and outcome of each AE will be reported in subject listings.

11.4.3.2. Tympanometry, Otoscopic, and Audiometry

The tympanometry category (A, B-small volume and/or normal, B-large volume, or C) will be summarized by treatment group and study visit.

Observations recorded during the conduct of otoscopic exams will be descriptive in nature. The number and percent of subjects presenting with each otoscopic classification will be provided by treatment group and study visit. Where relevant, the number and proportion of subjects with changes in their otoscopic classification from Baseline to the endpoint visit will also be provided for each treatment group. Presence and absence of tympanic membrane perforations will be summarized by treatment group and study visit; the size of any tympanic membrane perforation will be classified as follows: pinhole; ≤25% of tympanic membrane; 25% to ≤50% of tympanic membrane; >50% of tympanic membrane.

Descriptive summary statistics for audiometric assessments of air and bone conduction thresholds at each frequency will be provided by treatment group and study visit. All audiometry assessments will be tabulated separately for the treated and untreated ear.

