9.1. Adverse Event Classification Definitions

Adverse Event:

An AE is any unfavorable and unintended diagnosis, symptom, sign, syndrome, or disease which occurs after administration of investigational product, having been absent at baseline, or, if present at baseline, appears to worsen.

This includes any occurrence that is new in onset or aggravated in severity or frequency from the baseline condition, including abnormal results of diagnostic procedures and/or laboratory test abnormalities, which are considered AEs if they:

- result in discontinuation from the study
- require treatment or any other therapeutic intervention
- require further diagnostic evaluation (excluding a repetition of the same procedure to confirm the abnormality)
- are associated with clinical signs or symptoms judged by the Investigator to have a significant clinical impact

Serious Adverse Event (SAE):

An SAE is defined as any untoward medical occurrence that:

- results in death,
- is life-threatening (Note: the term “life-threatening” refers to an event in which the subject was at risk of death at the time of the event rather than to an event which hypothetically might have caused death if it were more severe.),
- requires in-patient hospitalization or prolongation of existing hospitalization,
- results in persistent or significant disability/incapacity, or
- is a congenital anomaly/birth defect.

Medical and scientific judgment should be exercised in deciding whether expedited reporting is appropriate in other situations, such as important medical events that may not be immediately life-threatening or result in death or hospitalization but may jeopardize the subject or may require intervention to prevent one of the other outcomes listed in the above definition. These events should be considered serious.

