11.3.2. Safety Endpoints

The safety endpoints include:

- Incidence of treatment-emergent adverse events
- Change from Baseline in tympanometry
- Change from Baseline in otoscopy
- Change from Baseline in audiometry
- Change from Baseline in suicidal ideation or behavior
- Incidence of concomitant medications
- Change from Baseline in vital signs and weight

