11.4. Statistical Analyses

11.4.1. General

There will be two sets of analyses. The Primary analyses will be conducted after all subjects complete Week 8 of the study, with all planned analyses to be conducted with all data collected in the database at time of database freeze. There will be a final analysis conducted once all subjects complete Week 16 of the study, to include all data collected from all subjects across all time points.

All data collected will be summarized descriptively. Descriptive statistics for continuous data are number of subjects, mean, standard deviation, median, minimum, and maximum values. Descriptive statistics for categorical variables will include number of observations and percentages.

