14.6.1. Safety Review Committee

An independent Safety Review Committee will review accumulated individual safety data for the first 25% (35 subjects), 50% (70 subjects), and 75% (105 subjects) of subjects randomized and who have post-administration safety data. Blinded safety data including adverse events, concomitant medications, medical history, clinical safety laboratory measurements, audiometry, otoscopy, tympanometry, and C-SSRS data will be reviewed. The treatment assignment for an individual subject may be unblinded, if deemed necessary to enable medical care or study decision-making by the Safety Review Committee. The decision to continue with the study will be based recommendations from the Safety Review Committee on the clinical significance of any adverse events or suspected investigational product-related or procedure-related findings. Additional information on the Safety Data Review and composition of the independent Safety Review Committee is provided in the Safety Review Committee Charter.

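### The audiometry section specifies threshold statistics by arm and visit, although the endpoint is change from baseline, and no planned table counts how many subjects lost hearing in the injected ear

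*Combined protocol and SAP*

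**What the plan says.** Section 11.3.2 lists "Change from Baseline in audiometry" among the safety endpoints, as does the synopsis. Section 11.4.3 opens the safety analyses with a general rule: "All safety endpoints will be summarized descriptively using the safety analysis set". Section 11.4.1 defines what such a summary contains: "Descriptive statistics for continuous data are number of subjects, mean, standard deviation, median, minimum, and maximum values".

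The section specific to audiometry, 11.4.3.2, says: "Descriptive summary statistics for audiometric assessments of air and bone conduction thresholds at each frequency will be provided by treatment group and study visit". It adds that treated and untreated ears are tabulated separately. It names no change score, no criterion for a threshold shift, no count of subjects, no shift table and no listing.

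Other safety measures get more:
- Otoscopy (11.4.3.2) has a count of subjects whose classification changed from baseline.
- The C-SSRS (11.4.3.3) has a shift table and full listings.
- Laboratory values and vital signs (11.4.5) have change from baseline and, where appropriate, shifts.

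On adverse events, Section 9.1 covers "abnormal results of diagnostic procedures and/or laboratory test abnormalities, which are considered AEs if they" meet one of four conditions: discontinuation, treatment, further diagnostic evaluation beyond a repeat of the same test, or that they "are associated with clinical signs or symptoms judged by the Investigator to have a significant clinical impact".

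**The concern.** Hearing loss in the injected ear is an obvious local harm to look for after an intratympanic injection. If it occurs, it may affect a few subjects substantially rather than all subjects slightly. Group threshold statistics at each visit are a poor instrument for that pattern, because a few large losses are diluted across the arm.

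The general rule in 11.4.3 and the specific instruction in 11.4.3.2 also point to different tables, so a programmer following 11.4.3.2 alone would not produce the listed endpoint. At stake is whether the report can say how many subjects in each arm lost hearing. If no criterion is fixed in advance, any such count would be defined after the data are known.

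**Working it through.** **The plan's own figures.** The plan gives no figure for audiometric change. The only design number used here is 70 subjects per arm (Section 11.5).

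**Step 1: dilution in the arm mean.** Shift in mean = (number affected × loss in dB) / n. The losses are assumed, because the plan defines no criterion.
- One subject losing 30 dB: 1 × 30 / 70 = 0.43 dB
- Three subjects losing 20 dB: 3 × 20 / 70 = 0.86 dB
- Three subjects losing 30 dB: 3 × 30 / 70 = 1.29 dB
- Three subjects losing 30 dB with 60 rather than 70 measured: 3 × 30 / 60 = 1.5 dB

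A count would show the three subjects as 3/70 (4.3%).

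**Step 2: do the extremes show it?** A maximum of raw thresholds need not. Entry allows a pure tone average of up to 70 dB in the study ear (inclusion criterion 6), so the arm maximum may belong to someone with pre-existing loss. In a simulation of 70 subjects with assumed thresholds (mean 35 dB, SD 15 or 20 dB, limited to 0–90 dB), a subject who lost 30 dB became the arm maximum in about 37% and 22% of runs respectively. A maximum of change scores would show the largest loss at each frequency, but not how many subjects had one.

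**Step 3: what a count can detect.** The probability of at least one case among 70 is 1 − (1 − rate)^70. For assumed true rates of 1%, 2% and 5% this is 51%, 76% and 97%.

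**Step 4: which cut-off is usable?** Section 8.5.5 gives 7 air and 3 bone conduction thresholds. Table 1 and Section 8.5.5 give 4 post-dose visits. That is 10 × 4 = 40 comparisons per subject for a worst-value row at any frequency. I simulated subjects with no true change, a baseline shared across visits, and independent normal errors. The share crossing each line by noise, by assumed SD of the test-retest difference, was:

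| SD (dB) | at least 10 dB | at least 20 dB |
|---|---|---|
| 4 | 19% | below 0.1% |
| 5 | 52% | 0.1% |
| 6 | 77% | 1.6% |

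The 30 dB row is essentially unaffected. A worst-value row at 10 dB could therefore be mostly noise, while 20 and 30 dB remain readable.

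**Step 5: the other routes.**
- *Adverse events (9.1).* A shift without symptoms that leads to no treatment, discontinuation or work-up beyond a repeat audiogram is not an AE.
- *Safety Review Committee (14.6.1).* It sees individual audiometry, but blinded. Its last scheduled look is at 105 of 140 subjects, which leaves 35 without a scheduled review.
- *Ad hoc analyses (11.4.3).* These follow only if the descriptive summaries call for them, and those summaries are the insensitive ones.

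**The case against.** The strongest reply is that the plan already promises the change itself. Sections 11.3.2, 11.4.1 and 11.4.3 read together commit to a mean, SD, minimum and maximum of change from baseline. On that reading the largest loss at each frequency would be reported. This stands. A reader might infer that individual hearing losses could appear in no summary at all, and the documents do not support that. What remains is a mismatch between 11.4.3 and 11.4.3.2, and the absence of a count.

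Nor is the AE route shut to every symptom-free shift, because work-up beyond a repeat test makes it an AE. A 30 dB loss may well cause symptoms or prompt such work-up. The gap is narrower than it first looks, but it exists.

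It is also tempting to compare the 1.3 dB with the standard error of a between-arm difference in thresholds. With an assumed SD of 15–25 dB, that is SD × √(2/70), or 2.5–4.2 dB. This is the wrong yardstick. The plan makes no such comparison, and the same subjects are measured at baseline and later. Pre-existing loss therefore cancels in the difference between visit means, apart from missing data. The dilution argument does not need it.

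Finally, Section 11.1 leaves detailed methods to an SAP that may modify the analyses. No separate SAP text was available for review, so an added shift analysis cannot be ruled out. Where the protocol defers a specific item to the SAP, as for imputation (11.4.2.1) and medications of interest (11.4.4), it says so. It does not for audiometry.

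**Conclusion.** The point holds in a limited form. Section 11.4.3.2 does not match the listed endpoint or the general rule in 11.4.3. Even on the generous reading, no planned table reports how many subjects in each arm lost hearing in the injected ear. Three 30 dB losses among 70 would move an arm mean by about 1.3 dB but would be plain as 3/70 in a count.

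The dilution figure rests on an assumed size and number of losses and on 70 measured subjects per arm. The noise figures rest on assumed test-retest SDs of 4–6 dB with independent normal errors. The mismatch between the sections and the missing count rest on the text alone. This is an inexpensive improvement to safety reporting and does not affect the primary efficacy analysis.

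**What to change.** In Section 11.4.3.2, for the study ear:

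1. State that within-subject change from baseline is summarized per frequency, for air and bone conduction, at each post-dose visit.
2. Tabulate by arm the number and percent of subjects whose threshold worsened by a predefined amount, at each visit and at the worst post-dose value, and list those subjects. At least 20 dB and at least 30 dB at any frequency would serve as reporting bands. The sponsor may choose another criterion if it is fixed before unblinding.
3. Do not include a 10 dB row for any frequency at the worst value. A table of change in air-bone gap is optional.

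In the same edit, reconcile the instruction to tabulate the untreated ear with Section 8.5.5, which tests only the study ear after baseline.

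The cost is one or two extra tables and a listing from data already collected. An occasional unchanged subject will cross the 20 dB line by noise (under 2% for an assumed SD up to 6 dB).

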11.4.3.3. Columbia-Suicide Severity Rating Scale (C-SSRS)

The C-SSRS will be administered at each visit using the appropriate version i.e., “Baseline” or “Since Last Visit”.

The “Baseline” version of the C-SSRS captures both suicidal ideation and suicide behavior (lifetime). There are 5 suicidal ideation questions, each captured as yes/no for the subject’s lifetime. There are 4 suicidal behavior questions, each captured as yes/no for the subject’s lifetime. An additional question asks if suicidal behavior is present during the visit. All suicidal ideation and behavioral variables as outlined here will be tabulated overall and by treatment group.

The C-SSRS version used at visits subsequent to the Baseline Visit will be a modified version of the “Baseline” C-SSRS. This “Since Last Visit” version uses the same individual variables for

suicidal ideation and behavior assessed at Baseline to capture changes, if any, from previous assessments. In addition, overall suicidality (yes/no) will be defined as any suicidal ideation or behavior since the last visit.

All suicidal ideation and behavior variables will be tabulated overall and by treatment group using a shift table for interpretation of changes in C-SSRS results between baseline and post-baseline assessments. All C-SSRS data will be included in data listings.

11.4.4. Concomitant Medications

Incidence of concomitant medications of interest will be provided for each treatment group. The list of concomitant medications of interest will be provided in the SAP.

11.4.5. Laboratory Parameters, Vital Signs and Weight

The analysis of laboratory parameters and vital signs will include descriptive statistics for the change from baseline to the endpoint visit, change from Baseline for each visit (vital signs only). Where appropriate, analyses will also include shifts from Baseline to the endpoint visit. For laboratory values, the normal ranges will be used to determine the classifications. Values below the normal range will be classified as low, values above the normal range will be classified as high, and values within the normal range will be classified as normal.

11.5. Sample Size

The primary endpoint is the percentage of responders, where response is defined as achieving at least a 13-point reduction from baseline in the TFI total score at both Weeks 4 and 8. It was observed from the previous study (Study 313-201901) that the response rate for OTO-313 (0.32 mg) was 43% and 13% for placebo. Based on these results, the assumed rate of response for OTO-313 is 43% and 18% for placebo, which is the 13% observed response rate in previous study plus 5% inflation for potential placebo response.

Assuming a 2-sided test and level of significance of 0.05, 60 subjects in the placebo arm and 60 subjects in each of the OTO-313 arms will provide approximately 85% power to detect a treatment difference in favor of OTO-313. It is also assumed that an observed discontinuation rate of 15% will be observed, hence the total sample size is planned to be 140 subjects, 70 subjects per arm. These sample size calculations were conducted using EASTv6.5 software with a test for a difference in proportions between two groups.

12. INVESTIGATIONAL PRODUCT INFORMATION

12.1. Physical Description of Investigational Product

The investigational product administered to subjects will be OTO-313 and placebo. OTO-313 is supplied as a 1 mL sterile solution (1.6 mg/mL [0.16%] gacyclidine in medium-chain triglycerides) in a vial. Placebo is provided as a 1 mL sterile solution of 100% medium-chain triglycerides in a vial. The vials are provided as kits, and all kits must be stored at 2-8°C until use.

12.2. Directions for Use

OTO-313 and placebo syringes will be prepared in a clean, secure location at room temperature. Please refer to the Pharmacy Manual for detailed investigational product preparation instructions.

12.3. Packaging and Labeling

12.3.1. Packaging

All investigational product kits will be labeled with information that will meet the applicable regulatory requirements.

12.3.2. Labels and Labeling Instructions

A label will be affixed to each kit box indicating kit number and storage instructions. A label will be affixed to the OTO-313 and placebo vials indicating contents and storage instructions.

12.4. Management of Clinical Supplies

The clinical supplies will be managed by the IRT system; instructions will be provided to all sites. The IRT will create shipment requests that will be generated based on inventory thresholds that are set for each site. A shipment request will be generated by IRT and sent to the clinical supply vendor. Upon shipment and receipt of the clinical study material, the site personnel will acknowledge the shipment and identify any damaged, missing, or unusable kits so they will not be dispensed.

12.4.1. Storage of Kits

All kits will be stored in accordance with instructions on the investigational product label. All temperature excursions of the investigational product must be documented in the investigational product accountability log. Any excursions within the allowable temperature range and conditions should be documented, but the investigational product is still acceptable for use and dispensing to subjects. If any excursions are outside of these conditions, the investigational product should not be used to treat subjects. If this occurs, the individual preparing the investigational product should immediately quarantine the product and report the kit(s) as unacceptable for dispensing to IRT to remove it from inventory.

12.5. Investigational Product Accountability

It is the responsibility of the Investigator to ensure that all investigational product received at the site will be inventoried and accounted for throughout the study and the result recorded on the drug accountability form maintained in the Pharmacy Manual. The person responsible for preparing the syringe containing the investigational product will be instructed to return all original containers, whether empty or containing investigational product, when instructed by the study monitor to return. Investigational product returned by the clinical site staff will be stored and disposed of according to the Sponsor's instructions. Investigational product accountability will be verified by the study monitor during the study. Investigational product will be stored in a limited access area or in a locked refrigerator under appropriate environmental conditions.

The Investigator agrees not to supply the investigational product to any person other than sub-Investigators, designated staff and the subjects participating in the study. Investigational product may not be relabeled or reassigned for use by other subjects except under special circumstances approved by the Sponsor.

The Investigator will retain and store all original containers returned by the clinical site staff until these containers are inventoried by the study monitor. Unless otherwise instructed by the Sponsor, the Investigator agrees at the end of the study to return all original containers, whether empty or containing investigational product, to the Sponsor as instructed. The Investigator agrees to neither dispense the investigational product from, nor store it at, any site other than the study sites agreed upon with the Sponsor.

The Sponsor will ensure proper disposal of original containers empty or full of returned or unused investigational product. Appropriate documentation will be maintained. Permission may be granted for local disposal, with supporting documentation.

13. ETHICAL ASPECTS

13.1. Investigator Responsibilities

The Investigator is responsible for ensuring that the clinical study is performed in accordance with the protocol, the Declaration of Helsinki, as well as with the Note for Guidance on Good Clinical Practice (ICH/135/95), and applicable regulatory requirements. These documents set forth that the informed consent of the subjects is an essential precondition for participation in the clinical study. Activities assigned to the Investigator may be delegated by the Investigator to staff qualified by education, training, and experience. Delegation should be documented in the delegation log.

13.2. Institutional Review Board (IRB) and Ethics Committee (EC)

This study will be undertaken only after full approval of the protocol and addenda has been obtained from a designated IRB or EC and the Sponsor has received a copy of this approval.

The IRB or EC must be informed of all subsequent protocol amendments issued by the Sponsor.

Reports on, and reviews of, the study and its progress will be submitted to the IRB or EC by the Investigator at intervals stipulated in their guidelines.

13.3. Informed Consent

Each subject must give written consent and sign other locally required documents after the nature of the study has been fully explained. The consent form is typically signed at the Screening Visit (Visit 1) and must be completed prior to performance of any study-related activity. The consent form that is used must be approved both by the Sponsor and by the reviewing IRB or EC. The informed consent is in accordance with the Declaration of Helsinki, current International Conference for Harmonisation (ICH) Good Clinical Practice (GCP) guidelines, and Sponsor policy.

The Investigator must explain to potential subjects the aims and methods of the study. The Investigator must also explain potential discomfort, benefits, and risks of study participation. Subjects will be informed that they are free not to participate in the study and that they may withdraw consent to participate at any time. They will be told which alternative treatments are available if they decline to participate in the study. Subjects will also be told that declining to participate in the study will not prejudice future treatment. Finally, they will be told that their records may be examined by competent authorities and authorized persons, but that personal information will be treated as strictly confidential and will not be publicly available. Subjects must be given the opportunity to ask questions. After this explanation and before entry into the study, consent should be appropriately recorded by means of the subject's dated signature of the informed consent form. If a subject is unable to read, an impartial witness must be present during the entire informed consent discussion. The signature of the impartial witness on the informed consent form will certify the subject's consent. The subject should receive a signed and dated copy of the informed consent form.

